10.2. Populations for Analysis

The populations for analysis are provided in [Table 8](#).

Table 8: Populations for Analysis

| Population | Description |
|--------------|--|
| Safety | 
All participants who received the study treatment.
 
All safety analyses will be conducted using the safety population. In addition, the safety population will also be used for summary of demographics, baseline characteristics, and participant disposition.
 |
| PK-evaluable | 
All participants who received the study treatment and provided at least 1 postdose PK sample.
 
The PK-evaluable population will be used for all PK analyses.
 |

10.3. Level of Significance

This is an exploratory, Phase 1 study, and no formal efficacy hypotheses will be tested.

10.4. Statistical Analyses

10.4.1. Pharmacokinetic Analysis

The PK-evaluable population will be used for all PK analyses.

The PK parameters, as described in [Table 7](#), will be summarized by total radioactivity and INCB099280 concentration in plasma using descriptive statistics. Individual participant and group mean radioactivity-time profiles in blood and plasma and the INCB099280 concentration-time profiles in plasma will also be generated in both linear and semilogarithmic scales.

10.4.2. Excretion and Mass Balance

Radioactivity in urine and feces will be reported as the percentage of the administered radioactivity excreted at each time interval and the total percentage of dose excreted (cumulative recovery). The mass balance of administered radioactivity will be determined by the summation of the percentage of dose excreted in both urine and feces during the study period. Renal clearance of unchanged INCB099280 may be calculated based on metabolite profiling data.

10.4.3. Safety Analyses

Safety analyses will be conducted for the safety population. Adverse events will be coded by the MedDRA dictionary, and TEAEs (ie, AEs reported for the first time or the worsening of a pre-existing event after study treatment administration) will be tabulated by preferred term and SOC for all events, related events, and events of Grade 3 or higher. Quantitative safety variables (eg, laboratory assessments, vital signs) and their changes from baseline will be summarized with descriptive statistics. Clinically notable abnormal values will be flagged and tabulated based on predefined criteria.

The clinical laboratory data will be analyzed using summary statistics; no formal treatment group comparisons are planned. In addition, distributions of key laboratory parameters may be plotted over time; these values will also be classified into toxicity grades ([FDA 2007](#)) and tabulated. The baseline value for laboratory assessments will be the last nonmissing measurement obtained before administration of the INCB099280 tablet.

Descriptive statistics and mean change from baseline will be determined for each ECG and vital sign parameter at each assessment time. The baseline value for ECG assessments will be the predose ECG. The baseline value for vital sign assessments will be the last nonmissing measurement obtained before the administration of the INCB099280 tablet.

Electrocardiogram and vital signs results will be reviewed for clinically notable abnormalities according to predefined criteria (see [Table 9](#) and [Table 10](#), respectively). Participants exhibiting clinically notable ECG and vital sign abnormalities will be listed.

Table 9: Normal Ranges for Electrocardiogram Intervals

| Parameter | High Threshold | Low Threshold |
|-----------|----------------|---------------|
| QTcF | ≤ 450 ms | ≥ 295 ms |
| PR | ≤ 220 ms | ≥ 120 ms |
| QRS | ≤ 120 ms | ≥ 50 ms |
| QT | ≤ 500 ms | ≥ 300 ms |
| RR | ≤ 1500 ms | ≥ 600 ms |

Table 10: Normal Ranges for Vital Sign Values

| Parameter | High Threshold | Low Threshold |
|--------------------------|------------------|------------------|
| Systolic blood pressure | ≤ 140 mmHg | ≥ 90 mmHg |
| Diastolic blood pressure | ≤ 90 mmHg | ≥ 50 mmHg |
| Pulse | ≤ 100 bpm | ≥ 40 bpm |
| Temperature | ≤ 38°C | ≥ 35.5°C |
| Respiratory rate | ≤ 24 breaths/min | ≥ 10 breaths/min |

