7.2. Participant Withdrawal From the Study

Participants **must** be withdrawn from the study for the following reasons:

- The participant has a confirmed (confirmed by 1 repeat test) decline in eGFR of 35% or greater compared with the baseline value (screening or Day -1). The assessment is based on measurements of serum creatinine and subsequent calculation of eGFR using the site's preferred formula. This assessment is to be conducted at investigator discretion after screening.
- The participant has a confirmed (confirmed by 1 repeat test) prolongation of QTcF \geq 60 milliseconds relative to baseline (defined as Day 1 predose) or an absolute QTcF \geq 500 milliseconds.
- The participant has an elevation of ALT $> 3 \times$ ULN (confirmed by 1 repeat test).
- The participant has a serious or severe (Grade 3 or higher) AE.
- Consent is withdrawn.

Note: Consent withdrawn means that the participant has explicitly indicated that they do not want to be followed any longer; in this case no further data, except data in public domain, may be solicited from or collected on the participant.

- Further participation would be injurious to the participant's health or well-being, in the investigator's medical judgment.
- The study is terminated by the sponsor.
- The study is terminated by the local health authority or IEC.
- At the discretion of the investigator.

A participant **may** be withdrawn from the study as follows:

- If a participant is noncompliant with study procedures or study treatment administration in the investigator's opinion, the sponsor should be consulted for instruction on handling the participant.
- If, during the course of the study, a participant is found not to have met eligibility criteria, the medical monitor, in collaboration with the investigator, will determine whether the participant should be withdrawn from the study.
- An AE or laboratory abnormality occurs that, in the opinion of the investigator, may constitute a potential risk for continued participation by the participant.

A participant may withdraw from the study at any time at their own request or may be withdrawn at any time at the discretion of the investigator for safety, behavioral, compliance, or administrative reasons. If a participant requests to leave the CRU earlier than planned, they may be provided with sample pots for home collection of urine and/or feces; this would be decided on a case-by-case basis following discussion between the investigator and the sponsor.

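### The notable-ECG listing uses absolute limits only, so a QTcF rise that meets the Section 7.2 withdrawal threshold need not appear in it

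*Combined protocol and SAP*

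**What the plan says.** Section 10.4.3 says that ECG and vital sign "results will be reviewed for clinically notable abnormalities according to predefined criteria", and points to Table 9 for ECGs. It then says: "Participants exhibiting clinically notable ECG and vital sign abnormalities will be listed".

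Table 9 gives a high and a low limit for each interval. The QTcF row reads "QTcF | ≤ 450 ms | ≥ 295 ms". The other rows that bear on this point are "QT | ≤ 500 ms | ≥ 300 ms" and "RR | ≤ 1500 ms | ≥ 600 ms". All are absolute values; no row concerns change from baseline.

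The same section plans descriptive statistics and mean change from baseline for each ECG parameter at each assessment time, with the predose ECG as baseline.

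Section 7.2 says that participants must "be withdrawn from the study for the following reasons". One of those reasons is a QTcF prolongation, confirmed by one repeat test, of at least "60 milliseconds relative to baseline (defined as Day 1 predose) or an absolute QTcF" of 500 ms or more.

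**The concern.** The protocol treats a 60 ms individual rise in QTcF as important enough to end participation. Its own review of notable ECGs does not look for that rise. A value of 450 ms or below counts as normal there, however far it has moved from the participant's predose value.

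Safety is a secondary objective, and its endpoint in Table 4 refers explicitly to changes in ECGs. The listing is the planned output that identifies individuals with notable ECGs. The study report could therefore record a withdrawal for QTcF prolongation alongside a notable-ECG listing that omits that participant, and a reader would have to reconcile the two.

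**Working it through.** The plan gives no figure to reproduce. The check is whether the two thresholds can disagree.

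**Inputs**
- Table 9 upper limit for QTcF: 450 ms, with 450 itself inside the range.
- Section 7.2 change threshold: 60 ms or more above Day 1 predose.
- Section 7.2 absolute threshold: 500 ms or more.
- Baseline: the predose ECG in Sections 7.2, 8.3.4 and 10.4.3, so the definitions agree.
- Eligibility: exclusion criterion 5 concerns QTcF above 450 ms and sets no lower QTcF limit, so a baseline of 390 ms or less can be enrolled.

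**Change threshold.** A rise of exactly 60 ms stays inside the QTcF row if baseline + 60 ≤ 450, that is, if baseline ≤ 450 - 60 = 390 ms.

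| Baseline QTcF (ms) | After a 60 ms rise (ms) | QTcF row of Table 9 | Largest rise inside the row (450 - baseline, ms) |
|---|---|---|---|
| 340 | 400 | not flagged | 110 |
| 360 | 420 | not flagged | 90 |
| 380 | 440 | not flagged | 70 |
| 390 | 450 | not flagged | 60 |
| 391 | 451 | flagged | 59 |
| 400 | 460 | flagged | 50 |

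**Absolute threshold.** 500 > 450, so every value that meets the 500 ms criterion is already flagged. The gap concerns the change criterion alone.

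**Could the QT row catch the rise instead?** By Fridericia's formula, QT = QTcF × (RR / 1000 ms)^(1/3). QT after a 60 ms rise, against the Table 9 range of 300 to 500 ms:

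| RR (ms) | Baseline 360 | Baseline 380 | Baseline 390 |
|---|---|---|---|
| 600 | 354 | 371 | 380 |
| 1000 | 420 | 440 | 450 |
| 1200 | 446 | 468 | 478 |
| 1500 | 481 | 504 | 515 |

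For these baselines, QT stays within limits at every RR tested from 600 to 1200 ms. It passes 500 ms only at RR 1500 ms, the edge of the RR range, for baselines of 380 and 390 ms (for example 440 × 1.5^(1/3) = 504 ms). The QT row is not a dependable substitute.

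**Group summaries.** Take six participants, one with a change of +60 ms and five with none. The mean is 60 / 6 = +10 ms. The sum of squared deviations is 50² + 5 × 10² = 3000, so the SD is √(3000 / 5) = 24.5 ms. A maximum, if reported, is 60 ms. These statistics can show that a large rise occurred, but they do not identify the participant.

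**The case against.** The strongest reply is that Table 9 is an out-of-range check, while Section 7.2 is a withdrawal rule applied to individuals during the study. Nothing says that the two must share thresholds, and they do not contradict each other. That is correct, and it is why this is an improvement to a listing and not an error in the plan.

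A reader might infer that the rise would go unreported. The documents do not support that:
- Section 9.1 makes an ECG finding that worsens from baseline an adverse event if the investigator considers it clinically significant. Section 8.3.4 has a similar rule, and Section 10.4.3 tabulates treatment-emergent events.
- The withdrawal itself would enter the disposition summary in the safety population (Table 8).

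The first route depends on the investigator's judgment, and nothing says that the disposition summary will show the QTcF change. Neither puts the participant in the notable-ECG listing.

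A reader might also infer that a group mean is the only planned analysis of change. Section 10.4.3 plans descriptive statistics as well as mean change, without naming each statistic. With six or seven participants and two scheduled postdose ECGs each (4 hours, and discharge or early termination), a large value would be hard to overlook. These remain group-level summaries.

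Finally, the likelihood of the event may be low. Section 2.1.1 puts the hERG IC50 at about 300 times the unbound steady-state Cmax at 400 mg BID and reports no adverse findings in the monkey cardiovascular study. This bears on how often the gap would matter, not on whether it exists.

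**Conclusion.** The gap is real and minor. The listing can omit a QTcF rise of 60 ms or more that ends at 450 ms or below. This is possible for any baseline of 390 ms or less, apart from the corner case in which a very long RR takes QT above 500 ms. Such a rise triggers Section 7.2 only if one repeat test confirms it.

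The threshold arithmetic needs no assumption beyond the documents' own limits. How many participants could be affected cannot be stated, because the documents give no baseline QTcF distribution. Any share worked out from an assumed distribution would describe whose baseline leaves room for a missed flag, not the chance of an event.

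The effect is on the completeness of one safety listing. Participant protection, the primary endpoints and the PK results are untouched. The point takes no view on whether the withdrawal threshold is clinically right.

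**What to change.** In Section 10.4.3, with a matching row or footnote to Table 9, keep the absolute limits and add that any QTcF increase of 60 ms or more from the predose ECG will also be flagged and the participant listed. The reporting criterion then matches the change threshold that Section 7.2 already states, and every such rise is listed whatever its absolute value.

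No separate 500 ms flag is needed for detection, because any such value already exceeds 450 ms.

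The cost is one line of analysis text and one listing column for change from baseline. The ECGs and the baseline definition are already in the plan; no visit, measurement or clinical rule changes.

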10.5. Interim Analysis

No formal interim analysis is planned in this study.

11. SUPPORTING DOCUMENTATION AND OPERATIONAL CONSIDERATIONS

11.1. Investigator Responsibilities

- The Protocol, Protocol Amendments, ICF, IB, and other relevant documents (eg, advertisements) must be submitted to an IEC by the investigator. All documents must be reviewed and approved by the IEC and health authorities before the study is initiated. The sponsor will be responsible for submitting all documents in participating countries.
- The investigator is responsible for ensuring that the safety reports provided by the sponsor are reviewed and processed in accordance with regulatory requirements, the policies and procedures established by the IEC, and institutional requirements.
- Any amendments to the Protocol will require approval from both health authorities and the IEC before implementation of changes made to the study design, except for changes necessary to eliminate an immediate hazard to study participants.
- Any amendments related to the administration of radioactive substances will be reviewed by the ARSAC practitioner prior to submission to ARSAC as required by the current ARSAC guidance ([2023](#)). The ARSAC practitioner will also be notified of any amendments to the Participant Information Sheet, ICF, and Protocol.
- The investigator will be responsible for the following:
 - Recording and documenting AEs or laboratory abnormalities identified in the Protocol as critical to the safety evaluation and reporting them to the sponsor according to the reporting requirements specified in the Protocol.
 - Recording and documenting all AEs, unless the Protocol provides different guidance in [Section 9](#).
 - Reporting to the sponsor all SAEs occurring to participants treated by them in the clinical study unless the Protocol provides different guidance in [Section 9](#).
 - Reporting an SAE to the sponsor per [Section 9](#) procedures and timelines if they become aware of an SAE with a suspected causal relationship to the study treatment that occurs after the end of the study.
 - Providing written summaries of the status of the study to the IEC annually or more frequently in accordance with the requirements, policies, and procedures established by the IEC.
 - Notifying the IEC of SAEs or other significant safety findings as required by IEC procedures.
 - Ensuring (along with the sponsor) that the clinical study is conducted in accordance with the Protocol and with the principles of GCP.
 - Providing oversight of the conduct of the study at the site and adherence to GCP, IEC requirements, institutional requirements, and applicable laws and country-specific regulations.

- Assigning tasks among the members of the team of investigators in a way that does not compromise the safety of participants or the reliability and robustness of the data generated at the clinical study site.
- The investigator will adhere to the Protocol as described in this document and agree that changes to the Protocol procedures, with the exception of medical emergencies, must be discussed and approved, first, by the sponsor or its designee and, second, by the IEC. Each investigator is responsible for enrolling participants who have met the specified eligibility criteria.
- The investigator will retain the content of the clinical trial master file, essential documents, AE documentation, and medical and other study records in accordance with all local, national, and regulatory laws but for a minimum period of at least 30 years after completion or discontinuation of the study or as described in the final executed copy of the individual site agreement, or at least 2 years after the last marketing application approval in an ICH region and until there are no pending or contemplated marketing applications in an ICH region, or if not approved, 2 years after formal discontinuation of clinical development of the test article and the regulatory authority is notified, whichever is longer, to ensure the availability of study documentation should it become necessary for the sponsor or a regulatory authority to review.
 - The investigator must not destroy any records associated with the study during the retention period without receiving approval from the sponsor. The investigator must notify the sponsor or its designee in the event of accidental loss or destruction of any study records. If the investigator leaves the institution where the study was conducted, the sponsor or its designee must be contacted to arrange alternative record storage options.
 - All eCRF data entered by the site (including audit trail), as well as computer hardware and software (for accessing the data), will be maintained or made available at the site in compliance with applicable record retention regulations. The sponsor will retain the original eCRF data and audit trail.

11.2. Data Management

Data management will be performed in a validated EDC system. The investigator will be provided with access to an EDC system so that an eCRF can be completed for each participant.

The site will be provided with eCRF completion guidelines for instructions on data entry in the eCRF. The study monitor will reference the Monitoring Plan in order to ensure that each issue identified is appropriately documented, reported, and resolved in a timely manner in accordance with the plan's requirements. Other data outside the EDC system required in the study conduct of the Protocol, such as documents or results transmitted to the sponsor via a central laboratory or specialized technical vendors and as designated by the sponsor, will have their own data flow management plans, study charters, or biomarker plans, as applicable.

The sponsor (or designee) will be responsible for the following:

- Managing the integrity of the data and the quality of the conduct of the study, such as ensuring that study monitors perform ongoing source data verification to confirm that data entered into the eCRF by authorized site personnel are accurate, complete, and verifiable from source documents; that the safety and rights of participants are being protected; and that the study is being conducted in accordance with the currently approved Protocol and any other study agreements, ICH GCP, and all applicable regulatory requirements.
- Managing and reconciling the data generated and/or collected, including documents and results such as laboratory or imaging data analyzed centrally by a designated vendor of the sponsor.

The investigator will be responsible for the following:

- Recording, or ensuring the recording of, all relevant data relating to the study in the eCRF.
- Delivering, or ensuring the delivery of, all other results, documents, data, know-how, or formulas relating to the study to the sponsor or designee electronically and/or centrally (eg, laboratory data, imaging data, biomarker data, photographs, diary data) or as otherwise specified in the Protocol.
- Maintaining adequate and accurate source documents and study records that include all pertinent observations on each of the site's study participants. Source data should be attributable, legible, contemporaneous, original, accurate, and complete. Changes to source data should be traceable, should not obscure the original entry, and should be explained if necessary (eg, via an audit trail). Source data are, in general, all information in original records and certified copies of original records of clinical findings, observations, or other activities in a clinical study necessary for the reconstruction and evaluation of the study. Source data are contained in source documents (original records or certified copies).
- Verifying that data entries are accurate and correct by physically or electronically signing the eCRF.

- Maintaining accurate documentation (source data) that supports the information entered in the eCRF, sent to a central vendor designated by the sponsor, or as described in other study and data flow manuals.
 - Source documents provide evidence for the existence of the participant and substantiate the integrity of the data collected. Source documents are filed and available at the investigator's site. Examples of source documents are original documents, data, and records (eg, hospital records; electronic hospital records; clinical and office charts; laboratory notes; memoranda; participants' diaries or evaluation checklists; pharmacy dispensing records; recorded data from automated instruments; copies or transcriptions certified after verification as being accurate copies; microfiches; photographic negatives; microfilm or magnetic media; x-rays; participants' files; and e-records/records kept at the pharmacy, at the laboratories, and at medico-technical departments involved in the clinical study).
 - Data entered in the eCRF that are transcribed from source documents must be consistent with the source documents or the discrepancies must be explained. The investigator may need to request previous medical records or transfer records, depending on the study. Current applicable medical records must be available.
- Sending participants' data, either as unique samples, copies, or photographs, to be evaluated centrally or analyzed centrally, or both, by a qualified vendor designated by the sponsor.
- Permitting study-related monitoring, sponsor audits, IEC review, and regulatory inspections by providing direct access to source data and other relevant clinical study documents.
 - Monitoring: Qualified representatives of the sponsor or its designee, study monitors, will monitor the study according to a predetermined plan. The investigator must allow the study monitors to review any study materials and participant records at each monitoring visit.
 - Auditing: Qualified representatives of the sponsor or its designee may audit the clinical study site and study data to evaluate compliance with the Protocol, applicable local clinical study regulations, and overall study conduct. The investigator must allow the auditors to review original source records and study documentation for all participants.
 - Regulatory inspection: Regulatory authorities may conduct an inspection of the study and the site at any time during the development of an investigational product. The investigator and staff are expected to cooperate with the inspectors and allow access to all source documents supporting the eCRFs and other study-related documents. The investigator must immediately notify the sponsor when contacted by any regulatory authority for the purposes of conducting an inspection.

